12.3 ANALYSES OF SECONDARY EFFICACY ENDPOINTS

The secondary efficacy endpoints will be analyzed using the FAS population as the primary analysis population for superiority, and PPS the primary analysis set for non-inferiority.

Secondary endpoints will be tested using a fixed sequence approach to adjust for multiple endpoints comparing between pooled roxadustat vs. pooled placebo, unless otherwise specified. If a null hypothesis is rejected, the claim of roxadustat over placebo will be declared successful and the test will progress to the next comparison in sequence.

1. Ex-US submission only: Mean CFB in Hb averaged over 8 weeks of treatment at Weeks 28 to 36, without rescue therapy within 6 weeks prior to and during this 8-week evaluation period for the two treatment groups will be compared using an MMRM model with baseline Hb and eGFR as covariates and treatment group, visit, treatment*visit, and the other

- randomization stratification factors as fixed effects. The same strategy as that used in MMRM for primary endpoint will be used to choose variance covariance structure. Data up to visit of Week 52 will be included in the model. The estimates for difference of Hb CFB averaged over Weeks 28 to 36 between the two treatment groups will be generated from an estimate statement for Weeks 28 to 36. Superiority will be declared if the lower bound of the 2-sided 95% confidence interval of the difference between roxadustat and placebo exceeds 0. Missing values will be handled by the MMRM model.
2. Mean CFB in Hb averaged over Weeks 28 to 52 in a subgroup of subjects with baseline CRP>ULN for the two treatment groups will be compared using MI ANCOVA model with baseline Hb as a covariate and treatment group, visit, treatment*visit, and the above-mentioned stratification factors as fixed effects. Data up to visit of Week 52 will be included in the model. The estimates for difference of Hb averaged over Weeks 28 to 52 between the two treatment groups will be generated from an estimate statement from Visit Week 28 to 52. Superiority will be declared if the lower bound of the 2-sided 95% confidence interval of the difference between roxadustat and placebo exceeds 0.
 3. Proportion of subjects with Hb (averaged Weeks 28 to 36) ≥ 10 g/dL, without use of rescue therapy within 6 weeks prior to and during this 8-week evaluation period, will be compared using Cochran-Mantel-Haenszel (CMH) adjusting for the randomization stratification factors.
 4. To assess the effect of maintenance dosing frequencies, pairwise comparisons of roxadustat TIW (3A), BIW and QW (2A and 1A from the original and amendment 1 versions of the protocol) vs. pooled placebo (1P+2P+3P) will be performed in subjects treated with roxadustat who have achieved Hb response (achieved Hb ≥ 11 g/dL and Hb ≥ 1 g/dL at two consecutive visits) within the first 24 weeks of treatment, and were treated in the maintenance phase at dose frequencies of TIW, BIW, or QW after Hb response. The Hb levels of these patients will be analyzed by dose frequency during Hb maintenance phase vs pooled placebo for the following two endpoints in a fixed sequence:
 - Average Hb level over Weeks 28 to 36 in the roxadustat Hb maintenance dose frequency subgroup (e.g., TIW) vs pooled placebo using the same method for the US primary endpoint.
 - Proportion of subjects with Hb (averaged over Weeks 28 to 36) ≥ 10 g/dL in the roxadustat Hb maintenance dose frequency subgroup (e.g., TIW) vs. pooled placebo using the same method for the ex-US primary endpoint.
 - 1) Roxadustat TIW vs. pooled placebo,
 - 2) Roxadustat BIW vs. pooled placebo,
 - 3) Roxadustat QW vs. pooled placebo.
 5. Mean CFB in LDL cholesterol averaged over Weeks 12 to 28 for the two treatment groups will be compared using MMRM models with baseline LDL cholesterol as a covariate and treatment group, visit, treatment*visit, and the above-mentioned stratification factors as fixed

effects. The same strategy as that used in MMRM for Hb will be used to choose variance covariance structure. Data up to visit of Week 52 will be included in the model. The estimates for difference of LDL Cholesterol averaged over Weeks 12 to 28 between the two treatment groups will be generated from an estimate statement from Visit Week 12 to 28. Superiority will be declared if the lower bound of the 2-sided 95% confidence interval of the difference between roxadustat and placebo exceeds 0.

6. Time to rescue therapy (composite of blood/RBC transfusion, ESA use, and IV iron) in the first 52 weeks of treatment will be compared using Inverse Probability of Censoring Weighted (IPCW) model detailed in Appendix A or Cox Proportional Hazards model as deemed appropriate. The Cox regression model will adjust for baseline Hb, baseline eGFR and other randomization stratification factors. Hazard ratio and its associated 95% CI will be computed between the roxadustat group versus pooled placebo. Superiority will be declared if the upper bound of the 2-sided 95% CI of the hazard ratio does not exceed one. Proportion of subjects who received rescue therapy over the treatment period will be derived using Kaplan-Meier approach.
7. Mean CFB in the SF-36 Vitality subscore averaged over Weeks 12 to 28 for the two treatment groups will be compared using an MMRM model as outlined above. A subgroup of subjects with baseline vitality subscore below 50 will be analyzed as a sensitivity analysis.
8. Progression of CKD measured by rate of change in eGFR over time adjusted by baseline eGFR, censored at chronic dialysis or kidney transplant will be analyzed using random slope and intercept model. Annualized eGFR slope over time is estimated by a random slope and intercept model using all available eGFR values (one baseline and all post-treatment values up to End of Treatment Period or start of chronic dialysis or kidney transplant) adjusted by Baseline Hb, Region, CV history at Baseline and the interaction terms Baseline eGFR by time point and Baseline Hb by time point). All assessments collected after initiation of chronic dialysis or kidney transplant will be excluded from the analysis.
9. Time to blood/RBC transfusion in the first 52 weeks of treatment will be compared using Inverse Probability of Censoring Weighted (IPCW) model detailed in Appendix A or Cox Proportional Hazards model as deemed appropriate. The Cox regression model will adjust for baseline Hb, baseline eGFR and other randomization stratification factors. Hazard ratio and its associated 95% CI will be computed between the roxadustat group versus pooled placebo. Superiority will be declared if the upper bound of the 2-sided 95% CI of the hazard ratio does not exceed one. Proportion of subjects who received blood/RBC transfusion over the treatment period will be derived using Kaplan-Meier approach.
10. Mean CFB in the SF-36 PF subscore averaged over Weeks 12 to 28 for the two treatment groups will be compared using an MMRM model as outlined above. A subgroup of subjects with baseline PF subscore below 50 will be analyzed as a sensitivity analysis.
11. Mean CFB in MAP averaged over Weeks 20 to 28 for the two treatment groups will be compared using an MMRM model as outlined above with a non-inferiority margin of 5.

12. Time to (and proportion of subjects with) protocol defined worsened hypertension for the pooled roxadustat vs pooled placebo will be compared using the approach in #4 above. Hazard ratio and its associated 95% CI will be computed between the roxadustat group versus pooled placebo. Non-inferiority will be declared if the upper bound of the 2-sided 95% CIs of the odds ratio does not exceed 1.3. Superiority will be declared if the upper bound of the 2-sided 95% CI of the hazard ratio does not exceed one. The incidence rate per PEY by treatment group will also be reported.

In MMRM above, due to large amount of visits to include in the model, the unstructured covariance pattern model will be applied first. If the algorithm for unstructured covariance pattern does not converge, then the heterogeneous Toeplitz structure will be used instead. If this second model also does not converge, then the (homogeneous) Toeplitz structure will be tried, and finally compound symmetry as a covariance structure to achieve convergence. If none of them converge, first order autoregressive (AR (1)) as a covariance structure will be used to achieve convergence.

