	
Repeated Measures (MMRM) model will be used for missing data imputation in the primary analyses.
 
The primary efficacy endpoint for the US (FDA) submission will be analyzed using the MI ANCOVA model comparing Hb CFB to the average of Weeks 28 to 52, stratified by the baseline value and randomization stratification factors, in a fixed sequence procedure: 1) pooled roxadustat (TIW+BIW+QW) vs. pooled placebo, 2) roxadustat TIW vs. pooled placebo, 3) roxadustat BIW vs. pooled placebo, 4) roxadustat QW vs. pooled placebo. The latter are being performed to test the BIW and QW maintenance dosing frequencies that are enrolled from earlier versions of the protocol. If a null hypothesis is rejected, the claim of the tested roxadustat regimen over placebo will be declared successful and the test will progress to the next comparison in sequence. The model will contain terms for treatment arm, baseline measurement, visit, visit x treatment arm, and other stratification factors. The primary efficacy analysis will be based on the estimated difference in the overall mean effect between the two treatment groups throughout the evaluation period based on the MI ANCOVA model.
 
The hypothesis to be tested for the primary efficacy analysis is:
 
H₀: Hb CFB to the average of Weeks 28 to 52 in the roxadustat group = Hb CFB to the average of Weeks 28 to 52 in the placebo group
 
Versus
 
H₁: Hb CFB to the average of Weeks 28 to 52 in the roxadustat group ≠ Hb CFB to the average of Weeks 28 to 52 in the placebo group
 
H₀ will be tested at the two-sided alpha=0.05 level of significance and will be rejected if the p < 0.05 from the test.
 
The primary efficacy endpoint for the Ex-US submission will be analyzed using the Cochran-Mantel-Haenszel (CMH) test comparing pooled roxadustat (TIW+BIW+QW) to pooled Placebo (TIW+BIW+QW) stratified by the randomization stratification factors.
 
The hypothesis to be tested for the primary efficacy analysis is:
 
H₀: Hb responder rate in the roxadustat group = Hb responder rate in the placebo group
 
Versus
 
H₁: Hb responder rate in the roxadustat group ≠ Hb responder rate in the placebo group
 
H₀ will be tested at the two-sided alpha = 0.05 level of significance and will be rejected if the p < 0.05 from the test.

--	---

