9.4.3.1 Primary Efficacy Analysis

The primary efficacy endpoint will be analyzed using the ITT population as the primary analysis population and PPS population as a supportive analysis population.

For US (FDA) Submission

The primary efficacy endpoint for the US (FDA) submission is the Hb CFB to the average level during the evaluation period, defined as Weeks 28 to 52.

The planned treatment duration is at least 52 weeks. The rationale for choosing the specified evaluation period as the primary endpoint for US (FDA) submission is that one would expect to have achieved Hb correction by Week 28, and averaging it to Week 52 would be an accurate reflection of a longer term therapeutic effect of roxadustat.

The hypothesis to be tested for the primary efficacy analysis is:

H_0 : Hb CFB to the average of Weeks 28 to 52 in the roxadustat group = Hb CFB to the average of Weeks 28 to 52 in the placebo group

Versus

H_1 : Hb CFB to the average of Weeks 28 to 52 in the roxadustat group = Hb CFB to the average of Weeks 28 to 52 in the placebo group

A Multiple Imputation Analysis of Covariance model (MI ANCOVA) will be used to compare the roxadustat and pooled placebo groups in a fixed sequence procedure: 1) pooled roxadustat (TIW+BIW+QW) vs. pooled placebo, 2) roxadustat TIW vs. pooled placebo, 3) roxadustat BIW vs. pooled placebo, 4) roxadustat QW vs. pooled placebo. The latter are being performed to test the BIW and QW maintenance dosing frequencies that are enrolled from earlier versions of the protocol. If a null hypothesis is rejected, the claim of the tested roxadustat regimen over placebo will be declared successful and the test will progress to the next comparison in sequence.

H_0 will be tested at the two-sided alpha = 0.05 level of significance and will be rejected if the $p < 0.05$ from the test.

Hemoglobin values under the influence of a rescue therapy will not be censored in the primary analysis. The model will contain terms for treatment arm, baseline measurement, visit, visit by treatment arm, and other randomization stratification factors. The primary efficacy analysis will be based on the estimated difference in the overall mean effect between the two treatment groups throughout the evaluation period based on the MI ANCOVA model.

For Ex-US Submission

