Sample SAS code:

```
PROC MI data=xx out=xx seed=xx nimpute=200;
  by treatment;
  var treatment covariates Week1 ... Week 52;
  mcmc impute=mono;
run;
```

2. For each dataset from step 1, missing ending data (hemoglobin up through end of evaluation period) will be imputed using seed 472794. As a result, 200 imputed complete datasets will be generated.
 - Missing data at Week 1 will be imputed using the regression imputation model with baseline stratification factor, baseline and hemoglobin from Week 1, using the SAS PROC MI procedure with the REGRESSION option in the MONOTONE statement.

- The SAS PROC MI procedure will use data separately from each treatment subject to impute the missing data for a specific Week (i.e., only those that need the imputation for the Week). Since subjects from the different treatment groups for that Week are excluded from the step, they will not contribute to the imputation for the Week.
- Repeat for all other scheduled Weeks sequentially (Week 2 to the end of evaluation period). Subjects whose missing data were imputed for previous Weeks will contribute to the imputation for the current Week.

The regression imputation model includes an intercept and the slopes of the hemoglobin from previous Weeks and the stratification factors.

3. Analyze each imputed dataset using the analysis of covariance model (ANCOVA) using the mean of all observed or imputed Hb values within the evaluation period. The model will contain terms for baseline Hb and eGFR measurements as covariates and treatment arm and the other randomization stratification factors except baseline Hb (≤ 8 vs > 8) and eGFR as fixed effects.

Sample SAS code:

```
PROC MIXED data=xx;  
  class treatment categorical covariates;  
  model change_Week36 = treatment covariates / solution;  
  lsmeans treatment / diff cl;  
  ods output Diffs=lsdiffs LSMeans=lsm solutionF=Parms;  
  by _Imputation_ ;  
run;
```

4. Combine estimates from the results of each of the 200 ANCOVA runs using SAS PROC MIANALYZE.

Sample SAS code:

```
PROC MIANALYZE parms(classvar=full)=lsdiffs;  
  class treatment categorical covariates;  
  modeleffects treatment;  
  ods output ParameterEstimates=MIAN_ lsdiffs;  
run;
```

Report the results of the least-squares mean estimates of the change from baseline in hemoglobin during the evaluation period, the estimates of treatment effect (e.g. least-squares mean CFB in

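### SAP 12.3 item 2 gives MI ANCOVA visit and treatment-by-visit terms that contradict SAP 12.1, and states no within-subject covariance for an alpha-controlled endpoint

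*SAP*

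**What the plan says.** **SAP 12.3, item 2.** The endpoint is mean Hb change over Weeks 28 to 52 in the subgroup with baseline CRP above the ULN. The two groups "will be compared using MI ANCOVA model with baseline Hb as a covariate and treatment group, visit, treatment*visit", with stratification factors as further fixed effects. Data up to Week 52 enter the model, and the treatment difference "will be generated from an estimate statement from Visit Week 28 to 52". Superiority requires the lower limit of the two-sided 95% confidence interval to be above 0.

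**SAP 12.1, where MI ANCOVA is defined.** Each imputed dataset is analysed by ANCOVA "using the mean of all observed or imputed Hb values within the evaluation period". Baseline Hb and baseline eGFR are covariates; treatment and the remaining stratification factors are fixed effects. The sample PROC MIXED line is "model change_Week36 = treatment covariates / solution", with no visit term and no REPEATED statement. Its response name points to Week 36 rather than the Weeks 28 to 52 mean, but it is only sample code. Step 4 reads "Combine estimates from the results of each of the 200 ANCOVA runs using SAS PROC MIANALYZE".

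**Covariance.** Items 1 and 5 of SAP 12.3 say how the covariance structure is chosen. Item 2 does not. The list of structures that closes 12.3 is introduced as applying to the MMRM analyses.

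**Multiplicity.** SAP 5.3 and 12.3 test the primary and secondary endpoints in a fixed sequence at alpha 0.05.

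**Protocol, FDA primary endpoint.** The synopsis names MI ANCOVA and adds: "The model will contain terms for treatment arm, baseline measurement, visit, visit x treatment arm, and other stratification factors". Section 9.4.3.1 does the same: "The model will contain terms for treatment arm, baseline measurement, visit, visit by treatment arm, and other randomization stratification factors". The synopsis also keeps this: "Repeated Measures (MMRM) model will be used for missing data imputation in the primary analyses".

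**The concern.** A treatment-by-visit term cannot be estimated from one record per subject, so item 2 cannot be the model of SAP 12.1. A programmer has either to drop terms that are written down or to stack the visits, and the SAP does not say which.

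If visits are stacked, Hb values from one subject are correlated, and a model without a within-subject covariance counts them as independent information. PROC MIXED does this when no REPEATED or RANDOM statement is given, and the only code that the SAP supplies for MI ANCOVA has neither. The confidence interval would then be too narrow whatever the true effect, and under the null the test would reject too often.

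Item 1 of the sequence is for Ex-US submission only. For the FDA, item 2 is therefore the first secondary test after the primary endpoint, and a false pass would open the test that follows it.

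**Working it through.** **The plan's own figures.** The SAP states no power, standard error or correlation for this endpoint. Its Hb power statement for 35 versus 150 subjects (difference 0.75 g/dL, SD 1.2 g/dL, 90%) reproduces at 91% (0.915 by normal approximation, 0.912 by noncentral t). The SD cancels in what follows.

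**Inputs.**
- Visits in the contrast: every 4 weeks (protocol 7.1.2.4), so Weeks 28, 32, 36, 40, 44, 48 and 52, m = 7.
- Within-subject correlation ρ after baseline adjustment: not in the documents; assumed 0.3 to 0.8.
- Fraction of missing information L: not in the documents; assumed 0 to 0.4. SAP 13.1.2 suspects differential dropout.

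**Complete data.** With equal variances and exchangeable correlation, the variance of a subject's mean over m visits is (σ²/m)(1 + (m−1)ρ). Independent errors give σ²/m. The ratio of the literal SE to the correct SE is therefore

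r = 1/√(1 + 6ρ), and the actual two-sided type I error is 2(1 − Φ(1.96 r)).

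**After multiple imputation.** Between-imputation variance is added whatever covariance the analysis model uses. If it makes up a fraction L of the correct total variance, the ratio becomes √(r²(1 − L) + L).

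| ρ | L = 0 | L = 0.2 | L = 0.4 |
|---|---|---|---|
| 0.3 | 0.60 (24%) | 0.70 (17%) | 0.78 (12%) |
| 0.5 | 0.50 (33%) | 0.63 (22%) | 0.74 (15%) |
| 0.7 | 0.44 (39%) | 0.60 (24%) | 0.72 (16%) |
| 0.8 | 0.41 (42%) | 0.58 (26%) | 0.71 (16%) |

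Each cell is the SE ratio, with the two-sided type I error in brackets. For example, ρ = 0.3 gives r = 1/√2.8 = 0.598, and L = 0.4 then gives √(0.357 × 0.6 + 0.4) = 0.78.

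By symmetry, half of each error rate falls on the side that declares superiority. With complete data that is about 12% to 21%, against a nominal 2.5%.

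**Other correlation shape.** With first-order autoregressive correlation of 0.5, 0.7 or 0.9 between adjacent visits and complete data, the ratio is 0.64, 0.53 or 0.42 (type I error 21%, 30% or 41%).

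**Simulation.** Complete data, 100 versus 50 subjects (an assumed subgroup size), 1,500 runs at each of ρ = 0.3, 0.5, 0.7 and 0.8. The stacked model with visit and treatment-by-visit terms and independent errors rejected in 25%, 32%, 40% and 43% of runs. ANCOVA on the per-subject mean rejected in 4.1% to 5.1%. The point estimates were identical; only the standard error differed.

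**Records in the model.** Item 2 admits all visits up to Week 52, not only these seven. The seven are the contrast. With equal variances across visits the ratio is unchanged.

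**The case against.** The SAP nowhere states independent errors. Item 2 can be executed in three ways: reuse the per-subject mean of 12.1; fit a repeated-measures model to the imputed data with the covariance list given for MMRM; or fit stacked records with independent errors. Only the third inflates error. The wording of item 2 is close to the MMRM text of item 5, so it may be left over from an MMRM specification, though that is an inference. Also, if the true difference is near the planning value of 0.75 g/dL, a false pass is not the practical risk.

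Much of this stands. It makes the consequence conditional, but it does not remove the contradiction. Where the SAP wants the primary method for another endpoint it says so, as in item 4; item 2 does not. The MMRM covariance list does not reach an analysis called MI ANCOVA, and SAP 12.2 treats the two as different analyses. A prespecified confirmatory test should not depend on which way a programmer resolves the conflict, and the interval width matters even when the effect is real.

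Three stronger readings are tempting, and the documents do not support them.
- **That the plan halves the standard error.** This needs independent errors, ρ of about 0.5 and almost no missing information. None of these is in the documents.
- **That a false pass opens every later test.** Under a fixed sequence it opens only the next one, and each later endpoint must itself be rejected at 0.05.
- **That the FDA primary analysis is affected.** SAP 12.1 gives its model, steps and code without visit terms. Protocol 9.5 expects significant changes to be highlighted in the SAP, and protocol 9.4.3 applies MMRM handling only where nothing else is specified. The protocol wording is stale, but the error rates above do not carry over to that analysis.

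**Conclusion.** The concern holds as a specification error. Item 2 names a model that cannot be fitted to the data structure of SAP 12.1, and it gives no within-subject covariance for an alpha-controlled test.

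The size is conditional on a literal fit to stacked visits with independent errors. Across the assumed correlation of 0.3 to 0.8, the standard error would be about 0.60 to 0.41 of the correct value with complete data (two-sided type I error about 24% to 42%). At the mildest corner examined, ρ = 0.3 with 40% missing information, it would be about 0.78 (about 12%). Under either of the other two ways of running item 2, this standard-error inflation does not arise.

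The contradiction is certain from the text. The numbers rest on assumed correlations and missing-information fractions. The wording should be settled before database lock.

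**What to change.** **In SAP 12.3, item 2:**
- Apply steps 1 to 4 of SAP 12.1 to the per-subject mean Hb change over Weeks 28 to 52, in the analysis population of 12.3. Name that population: 12.3 says FAS for superiority, while 5.2.4 says ITT for the FDA.
- Add the baseline CRP group to the imputation model, or impute within the CRP > ULN subgroup. The 12.1 imputation model does not contain CRP. Imputing everyone without it and then selecting the subgroup can pull imputed values toward the whole-arm pattern.
- In the CRP > ULN subgroup, fit ANCOVA with treatment, baseline Hb, baseline eGFR, region and cardiovascular history.
- Delete visit, treatment-by-visit and the sentence on the ESTIMATE statement.

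**For the FDA primary endpoint:** record in the SAP that 12.1 supersedes the visit terms in protocol 9.4.3.1 and the synopsis, and the synopsis sentence on MMRM imputation. Align the protocol text at the next amendment.

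**Cost:** SAP wording and the matching programming specification, with no new data. A protocol amendment for this alone is unnecessary; protocol 13.2 requires IRB/IEC approval before an amendment is implemented, so the alignment can wait for one made for other reasons.
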